10.2 Data Collection

Adverse events, device deficiencies, and serious adverse events shall be recorded on the CRF.

10.3 Reporting

For the purposes of this study, all adverse events will be collected upon subject enrollment. All adverse events, device deficiencies and any other potential unanticipated safety concern shall be recorded and

ILLUMINATE Clinical Study Protocol

reported to the sponsor on the appropriate CRF according to the reporting table below. Details of reporting and analysis are described in the statistical analysis plan (Refer to [REDACTED] ILLUMINATE clinical study Statistical Analysis Plan).

Safety Event	Reporting Timeframe	Report to Laborie	Report to local IRB (if applicable)
SAE	24 hours		In accordance with local IRB procedure if applicable
SADE		Email: 

	
AE	According to clinical site policy or as soon as reasonably possible.		
ADE			
Sponsor communication to Central IRB			
SAE		Laborie will communicate SAEs to Central IRB in accordance with the IRB policy	
SADE			

10.4 Foreseeable Events

The residual risks have been deemed acceptable and the benefits outweighs the risks. Please also refer to Section 5.0 above for assessment of risks and adverse device effects.

10.5 Follow-Up

If an adverse event occurs, any follow-up intervention prescribed is at the discretion of the Investigator, and the site must notify Laborie of the outcome of the follow-up.

11 STATISTICAL CONSIDERATIONS

[figure not shown]
11.1 Statistical Method

This is a descriptive study aimed at estimating parameters used in diagnostic evaluation of gastrointestinal disorders. No formal hypothesis tests are planned for any endpoint. Descriptive statistics will be used to analyze data from this study. Continuous variables will be summarized with means, median, standard deviations, IQR, sample size (N), minimums, and maximums. If included, categorical variables will be summarized in frequencies and percentages in the category of interest. Statistical analysis will be conducted using a validated statistical software package. A Statistical Analysis Plan outlining the details of the analyses and hypothesis testing is available [REDACTED] ILLUMINATE clinical study statistical analysis plan) and will be finalized prior to database lock.

ILLUMINATE Clinical Study Protocol**11.2 Sample Size Determination & Power**

The sample size is calculated for estimating the mean for specific parameters with a specified precision. Anal resting pressure was selected for calculating the minimum sample size as it is more indicative of catheter behavior and one of the main parameters of interest for physicians. Details are described in the statistical analysis plan (Refer to: [REDACTED] ILLUMINATE clinical study Statistical Analysis Plan).

Briefly, the sample size was determined based on the following formula and assumptions:

**11.3 Randomization / Blinding**

The ARM procedures during the study will be conducted in an open label setting so no blinding will be possible. Also, there will be no randomization. For all study subjects, the Solar catheter will be first in the order of catheter insertion during ARM procedures. The Solar catheter will be the first catheter that will be used in all study subjects, even for the subset of study subjects undergoing ARM procedures with both the Solar and UNITIP catheters. A washout period between procedures to be defined by the investigator in accordance with their standard of practice will be used to mitigate potential confounding impact of patient fatigue on the primary objective.

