3.2 Rationale

During ARM tests, catheter design and data analysis algorithms are known to affect absolute pressure values, with parameters measured by different types of sensors differing significantly (Emma V. Carrington et al. 2020; Banasiuk et al. 2022; Staller 2015). Consequently, normal reference values for these anorectal function parameters are critical for new catheters and systems for clinical translation of diagnostic data (Emma V. Carrington et al. 2020; E. V. Carrington et al. 2014; Lee and Bharucha 2016; Oblizajek et al. 2019; Sharma et al. 2021; Bharucha et al. 2022).

For this research study, two types of catheters will be used: an air charged catheter and a solid state catheter. First, the air charged catheter will be used in an ARM procedure on all study subjects. Afterwards, the solid state catheter will be used in a second ARM procedure on some of the study subjects to collect the same ARM measurements as the first procedure. Both types of catheters will use the Solar GI HRAM or Solar Compact HRM data collection and analysis system.

The air-charged catheter to be used is the “Solar™ Anorectal Manometry Catheter”.

As a new type of HRAM catheter design with air charged pressure sensors, establishing normal reference values for anorectal function parameters for the Solar catheter is critical for clinical translation of diagnostic data. Consequently, this clinical study is primarily designed to obtain normative datasets for traditional measures of anorectal function for the Solar catheter in asymptomatic subjects using the IAPWG standardized testing protocol and London classification. The first ARM procedure using the Solar catheter on all study subjects is designed to achieve this.

ILLUMINATE Clinical Study Protocol

The solid state catheter to be used is the “UNITIP™ Solid State High Resolution Anorectal Manometry” catheter, or “UNITIP” catheter. The UNITIP catheter is a reusable HRAM catheter developed by Laborie and has been on the market since 2008.

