The Solar catheter and the UNITIP catheter are Laborie-designed HRAM catheters with different types of pressure sensors that use the same data analysis algorithms in the Laborie Solar GI HRAM or Solar Compact HRM system. It is important to understand the relative performance of the two types of catheters when determining traditional anorectal function parameters. Therefore, a secondary rationale for the clinical study is to qualitatively compare the performance of the Solar catheter and the UNITIP catheter in determining values for traditional measures of anorectal function in a subset of the study subjects using the IAPWG standardized testing protocol and London classification. To achieve this, a second ARM procedure with the UNITIP catheter will be carried out on some of the study subjects under the IAPWG standardized testing protocol and London classification. Measurement values obtained from the second ARM procedure will be qualitatively compared to that from the first ARM procedure to understand the relative performance of the two catheters.

ILLUMINATE Clinical Study Protocol**3.3 Medical Device**Solar Catheter [REDACTED]

[REDACTED]

[REDACTED]

[REDACTED]

ILLUMINATE Clinical Study Protocol

[REDACTED]

[REDACTED]

[REDACTED]

ILLUMINATE Clinical Study Protocol

UNITIP™ HRAM Catheter

[REDACTED]

[REDACTED]

[REDACTED]

[REDACTED]

ILLUMINATE Clinical Study Protocol

Solar GI HRAM system

[REDACTED]

[REDACTED]

[REDACTED]

ILLUMINATE Clinical Study Protocol

Solar Compact HRM System [REDACTED]

[REDACTED]

[REDACTED]

[REDACTED]

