This is a prospective, multi-center, open label post-market study. The treatment arm (i.e., ARM with Solar catheter) will consist of approximately 81 asymptomatic individuals (volunteers) recruited from the intended patient population. A subset of up to 40 study subjects will be evaluated with two ARM catheters (i.e., Solar and UNITIP catheters). The order of application of the two catheters will not be randomized. A washout period between procedures will be determined by the investigator according to their standard practice and used to mitigate potential confounding impact of patient fatigue on the primary objective.

ILLUMINATE Clinical Study Protocol**5.2 Duration**

The duration of each subject's participation in the study is one clinic visit, which will include the amount of time required for informed consent, screening, enrollment, and the ARM procedure(s) execution. This is estimated to be about 1 hour for subjects evaluated with one ARM procedure and about 2 hours for subjects evaluated with two ARM procedures.

There is no follow-up period planned for the study. However, if an adverse event occurs and is unresolved during the evaluation, a follow-up will occur through 30 days post-procedure or until resolution, whichever is earlier.

Expected total study duration will be about 12 months (about 1 year).

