9 ASSESSMENT OF STUDY DEVICE

9.1 Endpoints

OBJECTIVES	ENDPOINTS	JUSTIFICATION FOR ENDPOINTS
Primary		
To obtain normative datasets for traditional measures of anorectal function with an air charged HRAM catheter in healthy subjects using the IAPWG standardized testing protocol and London classification for ARM measurement.	(All study subjects): Measure normal traditional anorectal function parameters with an air charged HRAM catheter (i.e., Solar Catheter) and Laborie's Solar GI HRAM or Solar Compact HRM data and software analysis system using the IAPWG standardized testing protocol for ARM measurement and the London classification for anorectal function disorders.	An HRAM system consists of a catheter inserted into the anorectal area and a data analysis unit which displays the results of the pressure measurements. Due to differences in catheter designs and the methods used to summarize pressures, catheter-specific normal reference values are necessary for direct clinical translation of HRAM measurements. The intent is to provide physicians with the relevant data to guide clinical translation of pressure measurements and catheter selection decisions.
Secondary		
Qualitatively compare the performance of air charged and solid state HRAM catheters in determining normative values for traditional measures of anorectal function in a subset of study subjects using the IAPWG standardized testing protocol and London classification for ARM measurement.	(Sub-set of study subjects): Measure normal traditional anorectal function parameters with a solid state HRAM catheter (i.e., UNITIP catheter) and Laborie's Solar GI HRAM or Solar Compact HRM data and software analysis system using the IAPWG standardized testing protocol for ARM measurement and the London classification for anorectal function disorders.	Endpoints will be measured by recording specific anorectal pressure parameters in each healthy individual using Solar™ air charged catheter and UniTip™ solid state catheter. The goal is to compare the readings recorded for each parameter by both catheters in the same healthy individual.

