4.1 Randomization/Blinding

The ARM procedures during the study will be conducted in an open label setting so no blinding will be possible. Also, there will be no randomization. For all study subjects, the Solar catheter will be first in the order of catheter insertion during ARM procedures. The Solar catheter will be the first catheter that will be used in all study subjects, even for the subset of study subjects undergoing ARM procedures with both the Solar and UNITIP catheters. A washout period between procedures to be defined by the investigator in accordance with their standard of practice will be used to mitigate potential confounding impact of patient fatigue on the primary objective.

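### Solar is always first and UNITIP always second, so the paired comparison measures catheter plus order, and the washout is justified by the wrong objective

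*Protocol*

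**What the plan says.** **Order.** Protocol 5.1 states: "The order of application of the two catheters will not be randomized". Protocol 11.3 and SAP 4.1 fix the direction: "For all study subjects, the Solar catheter will be first in the order of catheter insertion during ARM procedures". Protocol 11.3 then applies this expressly to the paired subjects: "The Solar catheter will be the first catheter that will be used in all study subjects, even for the subset of study subjects" who have both procedures. Protocol 3.2 describes the same sequence: "Afterwards, the solid state catheter will be used in a second ARM procedure on some of the study subjects". The subset is up to 40 of about 81 subjects (Protocol 5.1, SAP 4).

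**Timing.** Everything takes place in one clinic visit. Protocol 5.2 estimates about 1 hour with one procedure and "about 2 hours for subjects evaluated with two ARM procedures". The washout length is left to each investigator's usual practice.

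**Reason for the washout.** SAP 4.1 says that it "will be used to mitigate potential confounding impact of patient fatigue on the primary objective". Protocol 5.1 and 11.3 and SAP 4 give the same reason.

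**Use of the paired data.** Protocol 3.2 says that the second-procedure values "will be qualitatively compared to that from the first ARM procedure to understand the relative performance of the two catheters". Protocol 9.1 and SAP 3.2.2 add that the comparison is made within the same person. No hypothesis test is planned for any endpoint (Protocol 11.1, SAP 4.2).

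**The concern.** The secondary objective asks how the two catheters perform relative to each other. The design answers a different question: how a first procedure with Solar compares with a second procedure with UNITIP. Squeeze, push and cough depend on the subject's effort, so tiring, learning the manoeuvres or adapting to the first insertion are all plausible reasons for a second set of readings to differ. Any such change would be read as a difference between sensors. It could also hide a real one, since its direction is unknown.

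The documents do recognise fatigue as a possible confounder, but they assign it to the objective that it cannot reach. As a result, no released text names order or fatigue as a limitation of the secondary comparison, which is where the limitation applies.

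**Working it through.** The plan gives no figure for the paired contrast, so there is none to reproduce. The target of 81 is not an input here.

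**1. What the contrast estimates.** For subject *i*, let *d_i* = UNITIP reading − Solar reading. Write τ for the catheter effect (UNITIP minus Solar) and π for the order effect (second minus first procedure).

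- Sequence Solar then UNITIP: E[*d*] = τ + π.
- Sequence UNITIP then Solar: E[*d*] = τ − π. No subject has this sequence.

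There is one equation and two unknowns. Catheter and position coincide in every pair, so no model can estimate τ separately. The bias in reading *d* as τ is π at any number of pairs. Both sequences would be needed, since the average of the two expectations is τ.

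**2. Random error beside that bias.** Input: n = 40 pairs, the maximum in Protocol 5.1. With SD_d the standard deviation of the paired differences,

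95% half-width = t(0.975; 39) × SD_d / √40 = 2.023 / 6.325 × SD_d = 0.32 SD_d.

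An order effect of about 0.3 SD_d would be as large as the whole random error.

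**3. Illustration under assumed order effects.** The documents give neither π nor SD_d, so π = *k* × SD_d is an assumption. The table shows how often a nominal 95% interval around the mean paired difference would contain the catheter effect τ (20,000 simulated studies, n = 40).

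| assumed *k* | fixed order, 40 pairs | balanced order, 20 + 20 |
|---|---|---|
| 0 | 95% | 95% |
| 0.1 | 90% | 95% |
| 0.2 | 77% | 95% |
| 0.3 | 55% | 95% |
| 0.5 | 13% | 95% |

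The half-width is 0.32 SD_d in both designs. The balanced column assumes no differential carryover.

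**4. What the washout can protect.** The events in a paired subject run in this order: Solar procedure, washout, UNITIP procedure. Protocol 3.2 says that the first, Solar procedure is the one designed to meet the primary objective. Those readings exist before the washout begins, so the washout cannot alter them. It can alter only the UNITIP readings, which serve the secondary objective. What shields the Solar readings from fatigue is that Solar comes first.

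**5. What is known of the gap.** By the estimates in Protocol 5.2, the extra time for a second procedure is about 2 − 1 = 1 hour. That hour has to hold both the washout and the UNITIP procedure. Neither length is stated.

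**The case against.** The strongest reply is that this is an open and sensible choice in a descriptive study. The fixed order is stated in both documents and makes every Solar reading a first-procedure reading, which is what a normative dataset needs. The comparison is called qualitative and nothing is tested. All of that stands, and it is why the order should stay. It does not rescue the label: side-by-side summaries carry the same order effect as a formal test would.

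A reader might infer more than the documents support:

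- *That the paired contrast is meant to steer the choice of catheter.* The aim to "guide clinical translation of pressure measurements and catheter selection decisions" is in Protocol 9.1, but in the row for the primary objective, where it justifies catheter-specific normal values. The secondary row makes no such claim.
- *That a paired analysis is missing.* SAP 5.5 is redacted after its first sentence and may contain one, or a stated limitation. Redacted text still could not separate catheter from order.
- *That false-positive error is inflated.* No test is planned, and the table above rests on assumed order effects. The harm is a misread contrast.
- *That gaps are short and differ between sites.* Investigator discretion allows this, but no gap is given.
- *That switching between data systems adds a further bias.* Two systems are permitted, but Protocol 3.2 says that both catheters use the same analysis algorithms, and Protocol 8.1 and 8.6 require the devices used to be recorded. Nothing suggests a switch within a visit.
- *That the second procedure cannot touch the primary analysis in any way.* This is true of the Solar readings. SAP 5.2, however, defines the Full Analysis Set by completion of the HRAM procedure without saying whether that includes UNITIP, so an incomplete second procedure might change who is counted.

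**Conclusion.** The point holds for the secondary objective. In up to 40 paired subjects catheter and order are completely aliased, so the whole of any order effect enters the contrast, at any sample size. Its size and direction are unknown; with 40 pairs it sits beside a 95% half-width of 0.32 SD_d. The secondary result cannot be read as catheter performance alone.

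The washout rationale is wrong as written in Protocol 5.1 and 11.3 and SAP 4 and 4.1, because the readings that it is said to protect are already complete. The primary Solar readings are sound on this point.

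The aliasing and the misplaced rationale follow from the stated order and need no numerical assumption. Only the coverage table does. A reader might conclude that the order must be randomised; the documents do not require that, because it would trade away part of what protects the primary data.

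**What to change.** Keep Solar first, and make these changes:

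1. **Secondary result** (Protocol 3.2, 4 and 9.1; SAP 3.1.2 and 3.2.2): define it as *first-procedure Solar versus second-procedure UNITIP; catheter and order effects are not separable*. Do not report it as catheter performance alone.
2. **Washout rationale** (Protocol 5.1 and 11.3; SAP 4 and 4.1): tie it to the secondary objective.
3. **Data collection**: record the start and end time of each procedure and the data system used for it, so that the interval can be reported.
4. **Summary**: unless the redacted part of SAP 5.5 already does so, give the within-subject mean difference with its 95% CI and the limits of agreement for each parameter, under the label in item 1. With 40 pairs, the 95% half-width around each limit is about 2.023 × √(1/40 + 1.96²/78) = 0.55 SD_d.

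The cost is wording, slightly more data entry and a narrower secondary conclusion. The primary data are untouched.

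Randomising order within the subset is an optional trade-off and not part of this fix. About 20 Solar readings would then come second. Assume about 73 completers (81 × 0.9 = 72.9). Dropping those 20 readings widens the normative interval by about 17% (√(73/53) = 1.17); with all 81 it is 15% (√(81/61) = 1.15). Keeping them unadjusted carries 20/73 = 27% of the order effect into the normative mean. Differential carryover would also have to be assumed absent.

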11.4 Analysis Population

All consented subjects, including screen fails will be considered in the Enrolled analysis population with Safety endpoint(s). Enrolled subjects initiating catheter insertion but not completing the ARM procedure will be considered in the Attempted analysis population, also with Safety as the endpoint(s). Enrolled

ILLUMINATE Clinical Study Protocol

subjects completing the ARM procedure will be considered in the Completed analysis population and will be analyzed for the study endpoints.

11.5 Handling Missing Data

All attempts will be made to limit the amount of missing data. If any CRFs are found to be incomplete, the study monitor will follow up as to the reason. No attempt will be made to impute missing data. If a data point is missing, that data point will not contribute to that portion of the analysis. The number of evaluable observations will be reported in each analysis so that the extent of missing data can be assessed.

11.6 Deviations

Any changes to the planned statistical analyses or additions to the endpoints analyzed will be documented and justified in the final report. Any other deviations or changes from the planned analyses deemed necessary due to violation of critical underlying statistical assumptions, data characteristics, or missing data will be clearly described in the clinical study report with justification and rationale.

11.7 Early Stopping

There are currently no criteria for stopping the study early on statistical grounds, however you may refer to Section 7.3 for details about suspension or premature termination for non-statistical reasons.

11.8 Interim Analysis

No interim analysis is planned for this study. However, interim data may be summarized for the purpose of providing reports for internal review and assessment.

12 DATA HANDLING & RECORD KEEPING**12.1 Direct Access**

The investigator/institution will permit trial-related monitoring, audits, IRB review, and regulatory inspections by providing direct access to the source data/documents as needed. Regarding the subjects' personal data including health data, such data is provided in a de-identified form wherever possible and not otherwise necessary.

12.2 Confidentiality & Security

All information disclosed or provided by the Sponsor (or any company/institution acting on their behalf), or produced during study, including, but not limited to, the Protocol, the CRFs, and the results obtained during the course of the study, is confidential. The Investigator or any person under his/her authority agrees to undertake to keep the information confidential. In particular, the Investigator undertakes (1) not to make the information accessible to third parties - directly or indirectly, in writing, orally or in any other way - without the prior written approval of the Sponsor, (2) to use it exclusively within the scope defined by this Protocol and (3) to take all necessary measures to prevent third parties from becoming aware of and exploiting the information (obligation to secrecy, non-use and security).

However, the submission of this Protocol and other necessary documentation to the IRB is expressly permitted, the IRB members having the same obligation of confidentiality. The Sub-Investigators shall be bound by the same obligation as the Investigator. The Investigator shall inform the Sub-Investigators of the confidential nature of the Study. The Investigator and the Sub-Investigators shall use the

ILLUMINATE Clinical Study Protocol

information solely for the purposes of the Study, to the exclusion of any use for their own or for a third party's account.

All data to Laborie will be confidential and all subject identifiers will be redacted before being sent to Laborie. Documents will be kept in a secure location and all digital information will be kept following local government regulations.

